5. RESEARCH INTERVENTION PLAN

5.1 Administration Schedule

Ad/PSA

All patients will receive three injections of 0.16 ml. (0.125 ml. vaccine + 0.035 ml. Gelfoam) of the Ad/PSA subcutaneously in the right thigh unless patient condition precludes the use of that leg, in which case the left thigh will be used for all three injections. The dose of the vaccine, based upon our results from the Phase I trial, will be 1 x 108 pfu (4.4 x 109 particles) in the Gelfoam matrix. The Gelfoam comes in sterile patient-ready packages. The virus will be suspended in sterile saline and the Gelfoam powder added in a ratio of 30 mg of powder per ml. of virus suspension. Injections will be spaced apart by 30 days, such that each patient will receive the vaccine on days 1, 30, and 60. The use of the matrix has been shown in collaborative pre-clinical experiments to enhance infection of host cells by the virus. Results from the Phase I trial indicated that the injection of the vaccine in Gelfoam did not produce any adverse events greater than those produced by the vaccine in an aqueous suspension. The vaccine induced anti-PSA immune response in patients injected as an aqueous or Gelfoam vaccination. Injections will be carried out in the University of Iowa Clinical Research Unit (CRU). Each subject will be required to stay in the CRU for two hours and observed for early signs of toxicities.

5.2 5.2 Design and Stages

The ideal design would be a two-stage design of Simon (1989) requiring 32 patients. But due to the complexity of the trial, a more conservative approach consisting of using 32 patients in a one-stage design at efficacy level and a two looks at toxicity level as means of stopping rules will be carried out. By using a one-stage design at efficacy endpoint, we are making the probability of early termination for efficacy purposes to be zero. The reason for this design is due to the nature of the research intervention as outlined in section 10. Stopping design based on toxicity is as follow: one look after 17 subjects are treated and another look after 25 subjects are treated. If 5 out of 17 show vaccine-related grade 3 toxicity or higher, the trial will stop. Otherwise, an additional 8 subjects will enter the trial. If 7 out of 25 show grade 3 toxicity or higher, the trial will stop otherwise we will proceed to full registration of 32 patients to assess efficacy.

6. Adverse Events

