6.2 Procedures of documentation of AEs

All AEs occurring during the study must be documented, regardless of the assumption of a causal relationship, on the respective AE CRF. All events which occurred after signed informed consent should be documented. The investigator should ensure that all events are recorded that occurred within at least 4 weeks after the last exposure to the study drug (through Day 90).

Documentation of AEs includes: date of onset and offset, intensity, frequency, seriousness, related interventions and outcome. The investigator will also evaluate the probability of a causal relationship of the adverse event to the study medication as being: "definite, probable, possible, unlikely, or unrelated."

All unanticipated problems involving risk to subjects or others, serious adverse events related to participation in the study and subject deaths related to participation in the study will be promptly reported bν [contact]),bν email ([contact]), or by [contact]) to the USAMRMC, Office of Research Protections, Human Research Protection Office. A complete written report will follow the initial notification. In addition to the methods above, the complete report will be sent to the U.S. Army Medical Research and Materiel Command, ATTN: MCMR-ZB-PH, [name].

The medical monitor is required to review all unanticipated problems involving risk to volunteers or others, serious adverse events, and all volunteer deaths associated with the protocol and provide an unbiased written report of the event. At a minimum, the medical monitor should comment on the outcomes of the event or problem, and in the case of a serious adverse event or death, comment on the relationship to participation in the study. The medical monitor should also indicate whether he/she concurs with the details of the report provided by the study investigator. Reports for events determined by either the investigator or medical monitor to be possibly or definitely related to participation and reports of events resulting in death should be promptly forwarded to the HSRRB.

Expedited reporting

The investigator must immediately report serious adverse events (SAE) occurring or observed during the course of the study and within 4 weeks of last administration of the study drug to the FDA, IRB, OBA, and CRU.

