the probability of early termination for efficacy purposes to be zero. Early termination will be based on toxicity only. The reason for this design is due to the nature of the research intervention and is explained below. Enrollment will not stop unless stopping rules based on toxicity are satisfied: "After the third vaccine dose is administered, toxicity will be evaluated 90 days into the trial"

Due to the nature of the research intervention, anti-tumor activity will be potentially delayed and the primary efficacy endpoint will be determined 18 to 20 months after initial patient accrual. Since we will be able to assess PSADT after nearly 20 months into the study, it will be unreasonable to stop the study due to unsatisfactory results prior to that point. This is the main reason why we will carry a one-stage design for the primary endpoint and a two-stage design for toxicity. Criteria for proceeding with enrollment into a subsequent stage prior to the two-year efficacy evaluation will be based on assessment of toxicity in the patient cohorts since this can be done as early as 90 days into the trial.

For toxicity purposes, we will test the null hypothesis that the toxicity level is less than 15% versus the alternative that it is greater than 35%. The trial will be stopped whenever the null hypothesis is rejected. We will conduct these tests in 2 different looks—one after an enrolment of 17 subjects and the second after 25 subjects are enrolled.

If 5 out of 17 show grade 3 vaccine-related toxicity or higher, the trial will stop (this will correspond to testing the toxicity hypotheses at level alpha=0.05 with a power 77%); otherwise, an additional 8 subjects will enter the trial. If 7 out of 25 show a grade 3 toxicity or if 2 out of 17 show a grade 4 toxicity or higher, the trial will stop (this will be equivalent to testing the toxicity hypotheses at level alpha =0.05 with a power 82%); otherwise we will proceed to full registration. The overall type I error for this test is 0.09. In addition, the trial will stop if any vaccine-related deaths occur. The determination of a death related to the vaccine will be made by the clinical trial team and an audit by the Data and Safety Monitoring Board.

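### The toxicity stopping rule does not define one event: look 1 requires vaccine-related toxicity, look 2 is silent on attribution, and sections 5.2 and 10 differ on grade at look 2

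*Combined protocol and SAP*

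**What the plan says.** Two sections give the rule.

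- **Look 1, 17 men.** Section 5.2: "If 5 out of 17 show vaccine-related grade 3 toxicity or higher, the trial will stop". Section 10: "If 5 out of 17 show grade 3 vaccine-related toxicity or higher, the trial will stop". The two agree: vaccine-related, grade 3 or above.
- **Look 2, 25 men.** Section 5.2: "If 7 out of 25 show grade 3 toxicity or higher, the trial will stop". Section 10: "If 7 out of 25 show a grade 3 toxicity or if 2 out of 17 show a grade 4 toxicity or higher, the trial" stops. Neither mentions attribution at this look. The grade wording differs, since the count in section 10 is only "If 7 out of 25 show a grade 3 toxicity", and the clause on 2 of 17 men with grade 4 appears only in section 10.

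Section 10 sets one pair of hypotheses for both looks: "the null hypothesis that the toxicity level is less than 15% versus the alternative that it is greater than 35"%. The looks are cumulative: "one after an enrolment of 17 subjects and the second after 25 subjects are enrolled". It states alpha 0.05 with power 77% for the first, alpha 0.05 with power 82% for the second, and an overall type I error of 0.09. It also stops the trial for any death related to the vaccine, and there it does name the attribution.

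Section 6.2 has every adverse event recorded "regardless of the assumption of a causal relationship" and rated on a five-level causality scale. No section says which of those levels make an event vaccine-related for the stopping rule.

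**The concern.** A stopping boundary works only if everyone who applies it counts the same events. Here two things are open.

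**Attribution.** A man among the first 17 whose grade 3 event was judged unrelated does not count at look 1. Whether he counts at look 2 cannot be settled from the text. The qualifier is missing in both sections, so it cannot simply be dismissed as a slip in one place. If unrelated events do count, look 2 compares vaccine toxicity plus background morbidity with limits that look 1 applies to vaccine toxicity alone.

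**Grade.** Sections 5.2 and 10 can give opposite decisions on the same 25 men.

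Section 10 makes toxicity the only ground for early termination, so this rule decides whether the trial reaches its planned efficacy assessment. The monitoring committee should not have to choose between readings with the data in front of it.

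**Working it through.** **Inputs.** From sections 5.2 and 10: boundaries of at least 5 of 17 and at least 7 of 25 (cumulative), with rates 0.15 and 0.35. Assumed, because the documents reviewed give no figure: a rate q of unrelated grade 3 or higher events per man, independent of related events.

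**1. The plan's own figures.** Exact binomial tails:

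| Look | P(stop) at 0.15 | Stated alpha | P(stop) at 0.35 | Stated power |
|---|---|---|---|---|
| ≥5 of 17 | 0.0987 | 0.05 | 0.765 | 77% |
| ≥7 of 25 | 0.0695 | 0.05 | 0.827 | 82% |

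Overall error with one event at both looks is P(X17 ≥ 5) + P(X17 < 5 and X25 ≥ 7) = 0.0987 + 0.0212 = 0.120, against the stated 0.09. The powers reproduce closely; the alphas do not. A normal approximation without continuity correction gives p = 0.048 at 5 of 17 and 0.034 at 7 of 25, which probably explains the stated 0.05. None of the variants tried gave 0.09.

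Both powers come from the same 35% rate, so the calculation assumes one event throughout. If look 2 also counted unrelated events at q = 0.05, its rate under the alternative would be 0.35 + 0.65 × 0.05 = 0.3825, and P(≥7 of 25) would be 0.899, not 0.82.

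**2. Look 2 read as all-cause.** Let r be the related rate. The any-cause rate is u = r + (1 − r)q. With x men having a related event among the first 17, and y of the remaining 17 − x having only an unrelated one:

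P(stop) = P(Bin(17, r) ≥ 5) + Σ over x = 0 to 4 and all y of P(Bin(17, r) = x) × P(Bin(17 − x, q) = y) × P(Bin(8, u) ≥ 7 − x − y).

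At r = 0.15:

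| q (assumed) | u | Stop at look 1 | Stop at look 2 | Total |
|---|---|---|---|---|
| 0 | 0.150 | 0.099 | 0.021 | 0.120 |
| 0.05 | 0.1925 | 0.099 | 0.119 | 0.217 |
| 0.10 | 0.235 | 0.099 | 0.283 | 0.381 |
| 0.20 | 0.320 | 0.099 | 0.637 | 0.736 |

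At r = 0.05, the chance of passing look 1 and then stopping at look 2 is 0.09% for q = 0.02, 0.8% for 0.05, 5.9% for 0.10, 19.1% for 0.15 and 39.2% for 0.20. It is about 0.01% when related events alone count.

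These figures cover the 5 of 17 and 7 of 25 counts only. They leave out the grade 4 clause and the stop for vaccine-related death, so they are not the full stopping probability of section 10.

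**3. Grade, by example.** Classify each man by his worst grade, and suppose that all events are vaccine-related. Among 25 men, six have grade 3 and one has grade 4.

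- Section 5.2: grade 3 or above = 6 + 1 = 7, so the trial stops.
- Section 10, read literally: grade 3 = 6, short of 7; grade 4 or above = 1, short of 2. The trial continues.

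**The case against.** The strongest reply is that the qualifier was meant to carry over. There is one hypothesis pair, both looks are called tests of it, and the powers reproduce on one rate. Section 8.5.1 shows the same habit: it describes toxicity as vaccine-associated, then drops the qualifier in a later sentence about the same events. Section 7.3 also uses toxicity to mean possible effects of vaccination. This stands. A reader might infer that look 2 counts events of any cause, but no section says so; the inference rests on a missing word. The text equally does not say that the qualifier carries over. Section 10 restates the attribution for deaths soon after leaving it out at look 2, and section 6 refers to 8.5.1 for a definition of dose-limiting toxicity that is not there.

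A reader might also infer that section 10 lets the most severe events go uncounted. That is too strong. Grade 4 and above has its own lower threshold, a vaccine-related death stops the trial, and the closing words on higher grades could be read as covering both clauses. What remains is that a grade 4 event may not count toward the 7.

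Finally, the larger probabilities depend on background rates that may be too high. Eligible men are asymptomatic, with negative scans or low PSA and slow doubling, and short life expectancy from comorbidity is excluded. Section 10 says that Phase I showed no significant adverse events. Part of the Phase I account was not in the text reviewed, so the plan cannot be faulted for lacking a rate. This also stands: the effect starts near zero.

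**Conclusion.** The concern holds as an inconsistency in the rule. Attribution is stated at look 1 and left open at look 2 in both sections. Grade at look 2, and the presence of a grade 4 clause, differ between sections 5.2 and 10, and seven affected men can produce opposite decisions.

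The documents do not support the stronger conclusion that the trial will stop a safe vaccine on unrelated events. That needs the all-cause reading, which is not stated, and a background rate, which is not given. On that reading, at a 15% related rate, the stopping probability rises from 0.120 to 0.217, 0.381 or 0.736 for assumed unrelated rates of 5%, 10% or 20%, with unrelated events independent of related ones. At a 5% related and 2% unrelated rate, the added risk is about 0.1%. On the other reading, with vaccine-related events at both looks, the powers hold, but the exact alphas are 0.099 and 0.070 and the overall error is 0.120, before the grade 4 clause is counted.

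**What to change.** Reconcile sections 5.2 and 10 so that both state the same rule, including:

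- one event definition for both looks, giving the grade and whether the event must be vaccine-related;
- if it must be, which levels of the section 6.2 causality scale count;
- whether the grade 4 clause applies, and if so its count, denominator and attribution.

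The sponsor and the monitoring committee should choose the definition; this review takes no position on it. Then recompute alpha, power and overall type I error exactly for the reconciled rule, with the grade 4 clause included if it is kept.

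The cost is a wording amendment in two sections and a short recalculation. Causality is already rated for each event, so no new data are needed. If vaccine-related events are chosen, look 2 will depend on an attribution judgement, as look 1 already does.

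### Section 5.2 omits two of section 10's toxicity stopping triggers (2 of 17 with grade 4 or higher, any vaccine-related death), and the stated error rates do not match the stated cut-offs

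*Combined protocol and SAP*

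**What the plan says.** Section 5.2 (Design and Stages) introduces its rule with "Stopping design based on toxicity is as follow". It then lists two cut-offs: "If 5 out of 17 show vaccine-related grade 3 toxicity or higher, the trial will stop" and, at the second look, "If 7 out of 25 show grade 3 toxicity or higher, the trial will stop". If neither is met, "otherwise we will proceed to full registration of 32 patients to assess efficacy". Its only pointer to section 10 concerns rationale: "The reason for this design is due to the nature of the research intervention as outlined in section 10".

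Section 10 (Statistical Considerations) tests a toxicity rate below 15% against one above 35%. It repeats the 5-of-17 and 7-of-25 cut-offs and adds two triggers. One is the second half of this condition: "If 7 out of 25 show a grade 3 toxicity or if 2 out of 17 show a grade 4 toxicity or higher". The other is a stop for any vaccine-related death, with relatedness decided by the trial team and audited by the Data and Safety Monitoring Board. Section 10 states alpha 0.05 and power 77% for the first look, alpha 0.05 and power 82% for the second, and an overall type I error of 0.09.

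The sections also define the looks differently. Section 5.2 has "one look after 17 subjects are treated and another look after 25 subjects are treated"; section 10 has "one after an enrolment of 17 subjects and the second after 25 subjects are enrolled".

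**The concern.** A trial-level stopping rule should give one answer for one set of data. Section 5.2 sits in the Research Intervention Plan, where a clinical team would look for conduct rules, and it ends in an unconditional instruction to continue. Suppose two of the first 17 men have grade 4 toxicity, fewer than five of those 17 have grade 3 or higher, and fewer than seven of 25 do. Section 10 stops the trial. Section 5.2 on its own goes on to 32 patients.

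Section 10 is not fully usable as it stands either:

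- The 2-of-17 trigger appears in the 25-patient sentence, so the look at which it acts is unclear.
- The looks count treated patients in one section and enrolled patients in the other, which affects timing and who is counted.
- In both sections the 5-of-17 count is limited to vaccine-related toxicity and the 7-of-25 count is not.

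At stake is whether more men are dosed after a cluster of grade 4 events, and whether the monitoring body is told the true chance of stopping.

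**Working it through.** **1. The two rules side by side**

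| Condition | Section 5.2 | Section 10 |
|---|---|---|
| 5 of 17, grade 3 or higher, vaccine-related | stop | stop |
| 7 of 25, grade 3 or higher (no attribution) | stop | stop |
| 2 of 17, grade 4 or higher | not mentioned | stop, look unclear |
| Any vaccine-related death | not mentioned | stop |
| None of the section's own conditions | continue to 32 | continue to full registration |

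**2. The plan's own figures**

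Inputs from section 10: p0 = 0.15, p1 = 0.35, cut-offs 5 of 17 and 7 of 25. The exact single-look probability is P(X ≥ r), with X ~ Binomial(n, p).

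| Look | Exact alpha (p = 0.15) | Stated | Exact power (p = 0.35) | Stated |
|---|---|---|---|---|
| ≥5 of 17 | 0.0987 | 0.05 | 0.765 | 77% |
| ≥7 of 25 | 0.0695 | 0.05 | 0.827 | 82% |

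Power agrees and alpha does not. Cut-offs of 6 and 8 would give alpha 0.032 and 0.025 but power 0.580 and 0.694, so 5 and 7 are the intended boundaries. They follow from a one-sided 0.05 normal approximation, n·p0 + 1.645·√(n·p0·(1 − p0)):

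- n = 17: 2.55 + 1.645·√2.1675 = 4.97, rounded up to 5
- n = 25: 3.75 + 1.645·√3.1875 = 6.69, rounded up to 7

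**3. Overall type I error, grade 3-or-higher cut-offs only**

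P(X₁₇ ≥ 5) + Σ over x = 0 to 4 of P(X₁₇ = x)·P(X₈ ≥ 7 − x), at p = 0.15.

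- First look: 0.0987
- Second look, by x: x = 4 gives 0.1457 × 0.1052 = 0.0153; x = 3 gives 0.2359 × 0.0214 = 0.0050; x = 0 to 2 give 0.0008 together. Sum 0.0212
- Total: 0.0987 + 0.0212 = 0.120, against 0.09 stated

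Other routes do not give 0.09 either: independent looks, 1 − 0.95² = 0.0975; correlated normal looks at 1.645, 0.074; exact with 6 and 8, 0.043. At p = 0.35 the two-look stopping probability is 0.864.

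**4. How often the omitted grade 4 trigger changes the decision**

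Let p be the grade 3-or-higher rate and q the grade 4-or-higher rate. The documents give no q, so it is assumed to lie between 0.5% and 5%. All events are taken as vaccine-related. Among the first 17, let a be the number with grade 4 or higher and b the number with grade 3 only:

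P(a, b) = 17! / [a! b! (17 − a − b)!] · q^a · (p − q)^b · (1 − p)^(17 − a − b)

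Section 10 stops on grade 4 and 5.2 never stops with probability

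Σ over a ≥ 2, a + b ≤ 4 of P(a, b)·P(X₈ ≤ 6 − a − b).

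Adding this to 0.120 gives the full-rule stopping probability at p = 0.15.

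| q | Gap, p = 0.15 | Gap, p = 0.10 | Full-rule stopping probability, p = 0.15 |
|---|---|---|---|
| 0.5% | 0.0019 | 0.0026 | 0.122 |
| 1% | 0.0073 | 0.0102 | 0.127 |
| 2% | 0.0275 | 0.0378 | 0.147 |
| 3% | 0.0582 | 0.0789 | 0.178 |
| 5% | 0.1426 | 0.1874 | 0.262 |

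The final decision is the same whether the trigger acts at the first or second look. What changes is how many more men 5.2 alone could enter: at most 32 − 17 = 15, or 32 − 25 = 7. At p = 0.35 the trigger moves the stopping probability only from 0.864 to at most 0.873.

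**The case against.** The best defence is that this is an omission and not a pair of opposite commands. The cut-offs are identical, 5.2 never says that a grade 4 cluster or a death should be ignored, and the trial must be run under the whole protocol. On that reading 5.2 summarises and section 10 is the full rule. That is reasonable, and a team that combined the sections would stop. But nothing in the available text tells the team to combine them, and the closing instruction in 5.2 has no exception.

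A reader might infer that the plan allows dosing to go on after a vaccine-related death. The documents do not support that. Section 10 gives the decision to the trial team with a board audit, section 6.2 sends serious events and deaths to the medical monitor and the agencies, and section 4.6 provides for a hold. These safeguards make the death omission mainly a drafting matter. They are weaker for grade 4 events: section 8.5.1.1 removes the affected patient but gives no trial-level count.

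A reader might also infer that section 10 leaves grade 4 events out of the 7-of-25 count because it says grade 3 there. The phrase for higher grades can attach to both halves of that sentence, and 5.2 includes them expressly. The literal reading is implausible; the wording only needs tidying.

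Three further points stand. The gap is below 1% at grade 4 rates of 1% or less with a 15% grade 3-or-higher rate, and section 10 reports no significant adverse events in Phase I, although that was a single injection. A detailed monitoring plan is on file with the monitoring committee, and it may contain the counts; it was not available, and some protocol passages were also removed before review. Finally, the normal approximation explains the 0.05 per look, but not the 0.09.

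**Conclusion.** The mismatch is real and should be fixed. Section 5.2, read alone, omits two of section 10's triggers, and the visible text does not say which section governs. The grade 4 trigger is the one that matters in practice. At a 15% grade 3-or-higher rate, the chance that the two rules end in different decisions through that trigger is 0.002 to 0.143 over assumed grade 4 rates of 0.5% to 5%. The upper figure needs the 5% rate. The figures of 15 or 7 further men are ceilings that assume no other body intervenes.

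The error-rate problem is separate and does not rest on an assumed grade 4 rate: alpha is 0.099 and 0.070 against 0.05, and overall type I error is 0.120 against 0.09, before the grade 4 trigger. With the trigger, the probability of stopping at the null grade 3-or-higher rate is 0.122 to 0.262 over the assumed range. This error runs towards stopping too often, so it is not itself a safety hazard, and it should not be used to argue that the mismatch between sections is more serious.

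**What to change.** Make section 10 the single governing rule and reduce 5.2 to a cross-reference. In section 10:

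- Assign the 2-of-17 grade 4-or-higher trigger to the 17-patient look. Whether it should act as soon as it is met is a sponsor choice, to be confirmed.
- Write grade 3 or higher at both looks.
- Use one denominator, treated patients, at both looks.
- State one attribution rule for the toxicity counts.
- Keep the any-time stop for a vaccine-related death.
- Restate alpha as 0.099 (5 of 17) and 0.070 (7 of 25), and overall type I error as 0.120. Add the values that include the grade 4 trigger over a stated range of grade 4 rates. Power can stay as stated.

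The cost is amendment wording, a short recalculation and slightly less favourable stated error rates. The sample size does not change.
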